6.2.5 Completion/Final Evaluation

Visit 5 Day 71-78 (Day 56 of study drug)

Procedures Performed:

- Administer questionnaires (ACT, QOL, A2WR)
- Review conmeds, and AEs since the previous visit (V4)
- Review study drug compliance (pill count)
- Confirm medication washouts (reschedule if not met).
- GI side effect check list
- Vitals
- Urine Pregnancy Test (if applicable)
- Physical Exam
- Exhale Nitric Oxide (FeNO)
- Spirometry
- Perform Methacholine Challenge --- reschedule visit if FEV₁ is < 60% or 1.5 L
- Administer bronchodilator
- Methacholine Recovery Challenge
- Collect Blood for cytokines, biomarkers and eosinophil count
- Pre-dose Pharmacokinetic blood draw--**PK subgroup only.**
- Study Drug Dosing
- Pharmacokinetic blood draw (Time 0.5, 1, 2, 3, 4 & 8 hrs)—**PK subgroup only.**
- Collect study drug.

Any subjects who discontinue the study early will be contacted to determine the reason why. These reasons will be documented in the study binder. If termination occurs to lack of tolerance or adverse events related to the study drug or procedures, protocols for reporting adverse events will be followed as outlined below.

7. SAFETY ASSESSMENTS

Bronchodilator: (albuterol/salbuterol) will be available to be administered if the participant is uncomfortable from the effects of the methacholine challenge test, and also be used for reversibility testing after spirometry at V1. These drugs can lead to tremor, nervousness, tachycardia, palpitations and headache – these reactions are transient and rare (<5%) with the proposed doses used for this study, and if they occur, we will monitor the patient until they return to baseline. High doses may cause arrhythmias and hypokalemia: these are very unlikely with the doses used for this study.

Exhaled NO (FeNO): Exhaled breath will be collected from forced expirations using disposable mouthpieces for the online exhaled NO (Circassia) procedure described in the American Thoracic Society (ATS) guidelines. There are no known risks involved with breathing into the collection system.

GI side effects: Patients will be asked about the frequency and severity of GI symptoms including eructation, heartburn, nausea, bloating or indigestion.

Methacholine challenge: involves the inhalation of an agonist to induce bronchoconstriction and may induce the symptoms of an asthma exacerbation (chest tightness, dyspnea, coughing). The procedure is performed in a closely monitored clinical environment, with availability of bronchodilator. This procedure has been safely used in many previous studies by our group; we will only perform this procedure if the baseline FEV₁ is > 60% predicted.

Questionnaires and assessments: Participants will be asked to provide information about their psychological, physical, and medical functioning on questionnaires.

Asthma Control Test (ACT). The self-administered validated ACT will be used for this measurement.

Juniper mini-Asthma specific quality of life (mini AQOL). Disease specific quality of life will be measured via the Juniper mini-Asthma Quality of Life questionnaire, a validated questionnaire.

2 week recall questionnaire: The Asthma two week recall (A2WR) was developed to capture the inherent intensity of the disease in individuals with asthma. It quantifies severity by combining information about impairment, risk, and the amount of medication required to maintain control.

Pulmonary Function Testing: requires deep and forceful respiratory efforts. It is a commonly performed and safe examination that is widely performed in patients with lung disorders. Some patients report chest soreness the day following the procedure. Some patients may experience light-headedness during the forced expiration. The risk of syncope is mitigated by having the patient perform the test in the seated rather than standing position.

Venous Blood Draw: For each blood draw, approximately 10 ml of venous blood will be drawn by phlebotomy from an upper extremity. For patients who consent to the pharmacokinetics study, an additional 105 ml of blood will be required. Blood drawing may cause a small amount of pain. In addition, a temporary bruise may develop. Rarely, people faint after blood drawing. Very rarely, the vein in which the needle has been inserted may become inflamed or infected.

Ginger is widely used as an over-the-counter dietary supplement. The formulation and amount of ginger used in this study (**2g per day**; Pure Encapsulations®) has been chemically characterized by HPLC and has been administered to patients at the oral amount (2 grams) for 28 days in multiple human studies measuring inflammatory mediators in colonic mucosal biopsies. The incidence of side effects in a 28 day trials of 30 individuals were not significantly different in placebo versus ginger and no adverse events were greater than the NCI Common Toxicity Criteria Grade 1. In a second study of 27 individuals no adverse event greater than NCI Common Toxicity Criteria Grade 1 was reported (no placebo comparison) and the leading complaints were gastrointestinal symptoms of eructation, heartburn or indigestion.⁷ In a third study of 20 patients consuming the same formulation in the same amount for the same duration (2g, Pure Formulations, 28 days) no statistically significant increase in adverse events occurred compared to placebo, no toxicities were greater than the NCI Common Toxicity Criteria Grade 1 and included bloating, nausea and heartburn.¹⁶

There have been small numbers of studies reporting on possible inhibition of platelet aggregation by ginger. Ginger has been shown in an in vitro study to inhibit platelet aggregation with a potency similar to that of aspirin and in another study of human volunteers, to have a synergistic effect with nifedipine in platelet aggregation.⁸⁻¹⁰ A single case report has been published demonstrating epistaxis in a woman who was being treated with Coumadin who subsequently started taking ginger.¹¹ Subjects taking anti-coagulation will be excluded from participation, though subjects taking aspirin alone will be included in the study since there have been no studies or reports of increased bleeding risk with aspirin and ginger combined.

7.1 Specification of Safety Parameters

- ***Methacholine challenge*** involves the inhalation of an agonist to induce bronchoconstriction and may induce the symptoms of an asthma exacerbation (chest tightness, dyspnea, coughing). The procedure is performed in a closely monitored clinical environment, with availability of bronchodilator. This procedure has been safely used in many previous studies by our group; we will only perform this procedure if the baseline FEV₁ is > 60% predicted.
- ***Bronchodilator*** (albuterol/salbuterol) will be available to be administered if the participant is uncomfortable from the effects of the methacholine challenge test.
- ***GI side effects*** will be assessed at each study visit.
- ***Venous Blood Draw***: Rarely, people faint after blood drawing and therefore will be seated during blood draws. Very rarely, the vein in which the needle has been inserted may become inflamed or infected.

7.2 Methods and Timing for Assessing, Recording, and Analyzing Safety Parameters

● **Pulmonary function testing**: (spirometry or methacholine provocation) adverse effects are immediately apparent during the test and will be treated (albuterol inhaler) and recorded in the case report forms.

● **GI side effects**:^{7,16} This will be assessed at each study visit to ensure tolerance of the ginger capsules and will be recorded in the case report forms. Evidence of GI intolerance will be addressed as detailed in adverse events below.

● **Venous Blood Draw**: Rare fainting during blood draws occurs due to a vaso-vagal response and is immediately apparent. Subjects will have their blood pressure and heart rate assessed and will be monitored until they return to normal. Very rarely, the vein in which the needle has been inserted may become inflamed or infected. Blood draw sites will be inspected at each clinic visit.

7.3 Adverse Events and Serious Adverse Events

An Adverse Event (AE) is any unfavorable and unintended symptom, or disease temporally associated with the administration of ginger or the clinical testing proposed that may or may not be considered related to the medical treatment or procedure. Adverse events will be recorded regardless of their relationship to the study intervention.

Defining: A serious adverse event (SAE) is one that meets one or more of the following criteria:

- Results in death
- Is life-threatening (places the subject at immediate risk of death from the event as it occurred)
- Results in inpatient hospitalization or prolongation of existing hospitalization
- Results in a persistent or significant disability or incapacity
- Results in a congenital anomaly or birth defect

An important medical event that may not result in death, be life threatening, or require hospitalization may be considered an SAE when, based upon appropriate medical judgment, the event may jeopardize the subject and may require medical or surgical intervention to prevent one of the outcomes listed in this definition.

Adverse Event solicited and unsolicited:

Solicited at each study visit:

- Gastrointestinal side effects (including eructation, heartburn, nausea, bloating or indigestion)
- Venipuncture complications (swelling, infection)

Unsolicited at each study visit:

- Patients will have a general medical examination and vital signs at every visit.

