Ginger is widely used as an over-the-counter oral dietary supplement. The formulation and amount of ginger used in this study (2g per day; Pure Encapsulations®) has been chemically characterized by HPLC and has been administered to patients at the oral amount (2 grams) for 28 days in multiple human studies measuring inflammatory mediators in colonic mucosal biopsies. We chose this formulation and dose based on its history of excellent tolerance in previous human studies. We chose to divide the 2g dose into 1g twice a day dosing to minimize the chance of gastrointestinal side effects while limiting the burden on subject dosing to twice a day to increase retention and compliance within the study. We have also demonstrated in pre-clinical studies in a mouse model of asthma that this dose reduces asthma-associated lung inflammation.

The incidence of side effects in a 28 day trials of 30 individuals were not significantly different in placebo versus ginger and no adverse events were greater than the NCI Common Toxicity Criteria Grade 1. In a second study of 27 individuals, no adverse event greater than NCI Common Toxicity Criteria Grade 1 was reported (no placebo comparison) and the leading complaints were gastrointestinal symptoms of eructation, heartburn or indigestion.⁷ In a third study of 20 patients consuming the same formulation in the same amount for the same duration (2g, Pure Formulations, 28 days) no statistically significant increase in adverse events occurred compared to placebo, no toxicities were greater than the NCI Common Toxicity Criteria Grade 1 and included bloating, nausea and heartburn.

There have been small numbers of studies reporting on possible inhibition of platelet aggregation by ginger. Ginger has been shown in an in vitro study to inhibit platelet aggregation with a potency similar to that of aspirin and in another study of human volunteers, to have a synergistic effect with nifedipine in platelet aggregation.⁸⁻¹⁰ A single case report has been published demonstrating epistaxis in a woman who was being treated with Coumadin who subsequently started taking ginger.¹¹ Subjects taking anti-coagulation will be excluded from participation, though subjects taking aspirin alone will be included in the study since there have been no studies or reports of increased bleeding risk with aspirin and ginger combined.

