5.3 Concomitant Interventions

Required medications: Inhaled corticosteroids with or without long-acting beta agonists.

Allowed medications: Long acting anti-muscarinics, montelukast, or other medications not specifically excluded.

Prohibited medications: anti-coagulants such as warfarin, rivaroxaban and similar agents

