5.3.1 Allowed Interventions

Subjects will continue their usual asthma medications during the study except for the washout periods listed in section 4.1. Patients will continue their inhaled corticosteroids with or without inhaled long acting beta agonists and/or long acting anti-muscarinic medications. Additional asthma medications (e.g. montelukast) are also allowed. Rescue of asthma symptoms with short-acting beta agonists is also allowed and if this occurs within a washout period, the study visit will be re-scheduled. Subjects who are not excluded due to the use of anti-coagulants will continue the use of all other prescribed medications.

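### The protocol names a possible platelet and bleeding effect of ginger but does not solicit bleeding, and its wording on aspirin and other antiplatelet drugs needs reconciling

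*Combined protocol and SAP*

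**What the plan says.** **The risk.** Section 2.2 states: "There have been small numbers of studies reporting on possible inhibition of platelet aggregation by ginger". It adds an in vitro result of a potency similar to aspirin, a volunteer study reporting ginger "to have a synergistic effect with nifedipine in platelet aggregation", and this: "A single case report has been published demonstrating epistaxis in a woman who was being treated with Coumadin". Sections 5.1 and 7 (Safety Assessments) repeat the paragraph.

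**Who may enter.** The same paragraph excludes users of anticoagulants, "though subjects taking aspirin alone will be included in the study since there have been no studies or reports of increased bleeding risk" with the combination. Among drugs tied to bleeding, Section 4.2 (item 4), its copy in Section 6.2, and Sections 5.3 and 5.3.3 name only anticoagulants. Section 5.3 allows the listed asthma drugs "or other medications not specifically excluded". Section 5.3.1 adds: "Subjects who are not excluded due to the use of anti-coagulants will continue the use of all other prescribed medications".

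**What is asked.** Section 7.3 solicits five GI symptoms and "Venipuncture complications (swelling, infection". The checklist in Section 6.2, given at Visits 3, 4 and 5, covers the same five GI symptoms. Sections 7.1 and 7.2 cover methacholine and lung function testing, bronchodilator, GI effects and blood draws.

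**The concern.** A risk that the sponsor attributes to the study product is described three times, once inside the safety section, and then does not appear in any list of things to ask participants. GI symptoms, the other risk attributed to ginger, get a dedicated checklist. No reason is given for treating the two differently.

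At stake is the evenness and completeness of ascertainment. Capture of an unprompted event depends on whether a participant mentions it or whether it is still visible at the next visit, about four weeks later. Aspirin users are admitted because no reports of harm from the combination exist. Without a prompt, this placebo-controlled trial adds little to that evidence. Treatment lasts 56 days (Section 5.1), whereas the earlier tolerance experience cited is for 28 days.

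A second, smaller matter is that the rationale raises aspirin and nifedipine, but the medication rules mention neither.

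**Working it through.** The point rests on wording, so the main check is to set the sections side by side.

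**1. Is the risk named?** Yes, in Sections 2.2, 5.1 and 7.

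**2. Is bleeding or bruising prompted anywhere?**

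| Place | Content | Bleeding or bruising item |
|---|---|---|
| 6.2, GI checklist, Visits 3-5 | eructation, heartburn, nausea, bloating, indigestion | none |
| 7.1, safety parameters | methacholine, bronchodilator, GI, blood draw (fainting, inflamed or infected vein) | none |
| 7.2, methods and timing | lung function testing, GI, blood draw | none |
| 7.3, solicited events | GI symptoms; venipuncture swelling and infection | none |

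The venous blood draw text in Section 7 warns of a temporary bruise, yet bruising is not in the solicited venipuncture list.

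**3. What other route could capture a bleed?** Section 6.1 schedules adverse event review at all five visits and a physical examination at Visits 1, 3, 4 and 5. In Section 6.2 the complete examination includes nose and skin, and new abnormal findings become adverse events. Section 7.2 has draw sites inspected at each clinic visit. Section 7.3 records all events regardless of relationship. Section 10.3.5 has the monitors review event rates semi-annually. Bleeding is thus unsolicited, but it is not unmonitored.

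**4. Do the medication rules speak to the drugs in the rationale?** They name anticoagulants. Aspirin appears only in the rationale paragraph, where *alone* is not defined. Other antiplatelet drugs and nifedipine are not mentioned in any rule, so the default in Sections 5.3 and 5.3.1 applies to them.

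**5. How many participants?** 36 randomized 1:1 gives 36 / 2 = 18 on ginger. The PK subset is 8. The Précis describes 4 in Group A and 4 in Group B, which would put 4 on ginger. Sections 3, 6.2 and 6.2.4 describe 4 males and 4 females without giving the arms. Each PK participant has 6 post-dose samples at each of 3 visits, 6 × 3 = 18, and the first 6 follow a single dose. The documents do not give the share of participants on antiplatelet drugs or nifedipine.

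**6. What could a prompt show with 18 per arm?** Assume a placebo bleeding rate of 10% (not in the documents) and a two-sided Fisher exact test at 0.05. Power is the sum of the products of the two Binomial(18, p) probabilities over all tables with P ≤ 0.05:

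| Placebo | Ginger | Power |
|---|---|---|
| 10% | 20% | 6% |
| 10% | 30% | 20% |
| 10% | 40% | 43% |

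Solicitation would give descriptive counts, not a test.

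**The case against.** The strongest reply is that the plan already has several nets: adverse event review at every visit, scheduled examinations, draw-site inspection, recording of all events, and monitor review. This stands, and it rules out any claim that these participants go unwatched. It does not close the gap. Site inspection sees only the puncture site, and an examination about four weeks later may not show a nosebleed or bruise that has resolved. The protocol itself did not rely on general capture for GI symptoms.

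Second, the evidence is thin. The protocol speaks of possible inhibition from few studies, and its one epistaxis case involved a drug class that is already excluded. That argues for a light remedy, which this is.

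Third, the case report forms are an appendix that is not in the text available for review, so a bleeding item there cannot be ruled out. That stands as a limit. If the forms have one, Sections 6.2 and 7.3 need only be aligned with them.

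A reader might infer that the protocol restricts entry to aspirin-alone users and then contradicts itself by admitting every other antiplatelet user. The documents do not support that. The clause "though subjects taking aspirin alone will be included in the study" states an inclusion, not a restriction, and directly after the anticoagulant exclusion it can mean aspirin without an anticoagulant. Section 4.2 also excludes myocardial infarction or stroke in the last 3 months, and lists coronary disease and stroke as examples of exclusions at the physician's judgment. These would remove some antiplatelet users. The rationale states no limit on nifedipine users, so their entry contradicts nothing.

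**Conclusion.** The point holds as a gap in ascertainment: a bleeding effect is named as possible, but it is not in the solicited list, the checklist or the safety parameters. It concerns about 18 participants on ginger, 4 of them in the PK subset if the Précis split applies. How many take relevant co-medication is unknown and could be none.

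The medication part is an undefined term plus silence on other antiplatelet drugs and nifedipine. It is a request to reconcile wording, not a demonstrated contradiction.

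The point does not affect the primary analysis. It is a cheap improvement to safety data, and it assumes that the case report forms carry no bleeding prompt beyond what the protocol describes. A reader might also infer that a prompt would settle whether ginger raises bleeding. At this sample size, and at the assumed rates above, it would not.

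**What to change.** 1. Add bleeding, bruising and epistaxis to the solicited events in Section 7.3, and to the Visit 3-5 checklist in Section 6.2 and the matching case report form. The Visit 3 answer serves as the pre-treatment baseline.
2. Report descriptive counts by coded arm (A or B) to the independent monitors with the existing semi-annual adverse event review, and state that no powered comparison is intended.
3. Have the clinical team define aspirin alone and reconcile Sections 2.2, 5.1 and 7 with Sections 4.2, 5.3, 5.3.1, 5.3.3 and the copy of the criteria in 6.2. The documents should then state explicitly how other antiplatelet drugs and nifedipine are handled. Which rule to adopt is for that team.

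The cost is a few lines on a form already in use, some extra minor events recorded in both arms, and one wording clarification in the protocol.

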7.4 Reporting Procedures

Reporting: SAEs that are unanticipated, serious, and possibly related to the study intervention will be reported to the Independent Monitors(s), IRB, FDA, and NCCIH in accordance with requirements. To satisfy the requirement for prompt reporting, unanticipated problems will be reported using the following timeline:

- Unanticipated problems that are serious adverse events will be reported to the IRB within 48 hours and to the Independent Safety Monitor(s) and to the NCCIH within 7 days of the investigator becoming aware of the event.
- Any other unanticipated problem will be reported to the IRB, Independent Safety Monitor(s), and NCCIH within 14 days of the investigator becoming aware of the problem.

All unanticipated problems should be reported to appropriate institutional officials (as required by an institution's written reporting procedures), the supporting agency head (or designee), and OHRP within one month of the IRB's receipt of the report of the problem from the investigator.

Reporting to the FDA for the IND:

- 7-day IND Safety Report (unexpected fatal or life-threatening AEs related to the intervention); a copy of the report sent to the FDA will be submitted to the NCCIH Program Officer and Independent Safety Monitor(s) within 24 hours of FDA notification.
- 15-day IND Safety Report (any other serious and unexpected AE related to the intervention); a copy of the report submitted to the FDA will be submitted to the NCCIH Program Officer and Independent Safety Monitor(s) within 24 hours of FDA notification.
- All other AEs documented during the course of the trial will be reported to NCCIH on an annual basis by way of inclusion in the annual report and in the annual AE summary which will be provided to NCCIH and to the Independent Monitors. The Independent Safety Monitor(s) Report will state that all AEs have been reviewed.

7.5 Followup for Adverse Events

Subjects will be followed up as outpatients for adverse events that are not serious adverse events. Subjects will be followed up until symptoms of adverse events resolve. For serious adverse events, subjects will be followed up as an inpatient or outpatient as deemed appropriate by the treating physician. The follow up will continue until the adverse event is resolved or stabilized.

7.6 Safety Monitoring

[name] [name], a pulmonologist, and [name], a physician and epidemiologist, will serve as the data and safety monitors for the proposed study.

